Appendix 8 - Medications with Significant Arrhythmogenic Potential

Use of the following drugs is prohibited, due to the potential for QT interval prolongation. ^a	
	Setronax); Palonosetron (Aloxi); Tropisetron (Only on Non US Market) (Navoban, Setrovel)
Antifungal	Fluconazole (Diflucan, Trican); Pentamidine (Pentam)
Antihistamine	Astemizole (Removed from Market) (Hismanal); Terfenadine (Removed from Market) (Seldane)
Antihypertensive	Isradipine (Dynacirc); Ketanserin (Only on Non US Market) (Sufrexal); Moexipril/HCTZ (Uniretic, Univasc); Nicardipine (Cardene)
Antilipemic	Probucol (Removed from Market) (Lorelco)
Antimalarial	Artenimol+piperaquine (Only on Non-US Market) (Eurartesim); Chloroquine (Aralen); Halofantrine (Only on Non-US Market) (Halfan); Primaquine phosphate
Antimania	Lithium (Eskalith, Lithobid)
Antimycobacterial	Clofazimine (Only on Non-US Market) (Lamprene)
Antinausea	Domperidone (Only on Non-US Market) (Motilium, Motilium, Motinorm Costi, Nomit)
Antineoplastic agent	Inotuzumab ozogamicin (Besponsa); Oxaliplatin (Eloxatin)
Antipsychotic	Cyamemazine (cyamepromazine) (Only on Non-US Market) (Tercian); Haloperidol (Haldol [US & UK], Aloperidin, Bioperidolo, Brotopon, Dozic, Duraperidol [Germany], Einalon S, Eukystol, Halosten, Keselan, Linton, Peluces, Serenace, Serenase, Sigaperidol); Levomepromazine (methotrimeprazine) (Only on Non-US Market) (Nosinan, Nozinan, Levoprome); Levosulpiride (Only on Non-US Market) (Lesuride, Levazeo, Enliva [with rabeprazole]; Mesoridazine (Removed from Market) (Serentil); Perphenazine (Trilafon, Etrafon/Triavil, Decentan); Pimozide (Orap); Pipamperone (Only on Non-US Market) (Dipiperon [E.U], Propitan [Japan], Dipiperal, Piperonil, Piperonyl); Prothipendyl (Only on Non-US Market) (Dominal, Largophren, Timoval, Timovan, Tumovan); Thioridazine (Mellaril, Novoridazine, Thioril); Benperidol (Only on Non-US Market) (Anquil, Glianimon)
Antipsychotic/antiemetic	Chlorpromazine (Thorazine, Largactil, Megaphen); Droperidol (Inapsine, Droleptan, Dridol, Xomolix); Promethazine (Phenergan)
Antipsychotic, atypical	Aripiprazole (Abilify, Aripiprex); Asenapine (Saphris, Sycrest); Clozapine (Clozaril, Fazaclo, Versacloz); Iloperidone (Fanapt, Fanapta, Zomaril); Melperone (Only on Non-US Market) (Bunil, Buronil, Eunerpan); Paliperidone (Invega, Xepilon); Pimavanserin (Nuplazid); Risperidone (Risperdal); Sertindole (Only on Non-US Market) (Serdolect, Serlect); Sulpiride (Only on Non-US Market) (Dogmatil, Dolmatil, Eglonyl, Espiride, Modal, Sulpor); Sultopride (Only on Non-US Market) (Barnetil, Barnotil, Topral); Zotepine (Only on Non-US Market) (Losizopilon, Lodopin, Setous and Zoleptil)
Antiretroviral	Efavirenz (Sustiva and others)
Antisense oligonucleotide	Nusinersen (Spinraza)
Antiviral	Rilpivirine (Edurant, Complera, Eviplera); Saquinavir (Invirase [combo])
Beta-3 adrenergic antagonist	Mirabegron (Myrbetriq)
Cholinesterase inhibitor	Donepezil (Aricept)

Use of the following drugs is prohibited, due to the potential for QT interval prolongation. ^a	
Cyclin dependent kinase inhibitor	Ribociclib (Kisqali)
Dopamine 2 and 5HT2a antagonist	Flupentixol (Only on Non-US Market) (Depixol, Fluanxol)
Dopamine agonist	Apomorphine (Apokyn, Ixense, Spontane, Uprima)
Estrogen agonist/antagonist	Toremifene (Fareston)
GI stimulant	Cisapride (Removed from Market) (Propulsid)
Glucosylceramide synthase inhibitor	Eliglustat (Cerdelga)
Gonadotropin receptor agonist/antagonist	Leuprolide (Lupron, Eligard, Viadur, Carcinil, Enanton, Leuplin, Lucrin, Procren, Prostap and others)
Gonadotropin releasing hormone agonist/antagonist	Degarelix (Firmagon, Ferring)
Histone deacetylase inhibitor	Panobinostat (Farydak); Romidepsin (Istodax); Vorinostat (Zolinza)
Imaging contrast agent	Perflutren lipid microspheres (Definity, Optison)
Imunosuppressant	Tacrolimus (Prograf, Advagraf, Protopic)
Kinase inhibitor	Ceritinib (Zykadia); Crizotinib (Xalkori); Dabrafenib (Tafinlar); Lapatinib (Tykerb, Tyverb); Nilotinib (Tasigna); Sunitinib (Sutent); Vemurafenib (Zelboraf)
Local anesthetic	Cocaine
Microtubule inhibitor	Eribulin mesylate (Halaven)
Muscle relaxant	Terodiline (Only on Non-US Market) (Micturin, Mictrol [not bethanechol]); Tizanidine (Zanaflex, Sirdalud); Tolterodine (Detrol, Detrusitol)
Norepinephrine reuptake inhibitor	Atomoxetine (Strattera)
Opioid agonist	Levomethadyl acetate (Removed from Market) (Orlaam); Methadone (Dolophine, Symoron, Amidone, Methadose, Physeptone, Heptadon)
Opioid receptor modulator	Buprenorphine (Butrans, Belbuca, Bunavail, Buprenex, Suboxone, Zubsolv)
Oxytocic	Oxytocin (Pitocin, Syntocinon)
Phosphodiesterase 3 inhibitor	Anagrelide (Agrylin, Xagrid); Cilostazol (Pletal)
Phosphodiesterase 5 inhibitor	Vardenafil (Levitra)
Progesterone antagonist	Mifepristone (Korlym, Mifeprex)
Proteasome inhibitor	Bortezomib (Velcade, Bortecad)
Psychedelic	Ibogaine (Only on Non-US Market)
Sedative	Dexmedetomidine (Precedex, Dexdor, Dexdomitor)

Use of the following drugs is prohibited, due to the potential for QT interval prolongation. ^a	
Selective D2, D3 dopamine antagonist	Tiapride (Only on Non-US Market) (Tiapridal, Italprid, Sereprile, Tialaread, Tiaryl, Tiaprim, Tiaprizal, Sereprid, Tiapridex)
Somatostatic analog	Pasireotide (Signifor)
Sphingosine phospate receptor modulator	Fingolimod (Gilenya)
Tyrosine kinase inhibitor	Bosutinib (Bosulif); Dasatinib (Sprycel); Osimertinib (Tagrisso); Pazopanib (Votrient); Sorafenib (Nexavar)
Vasoconstrictor	Terlipressin (Only on Non US Market) (Teripress, Glypressin, Terlipin, Remestyp, Tresil, Teriss and others)
Vasodilator, Coronary	Papaverine HCl (Intra-coronary)
Vesicular monamine transporter 2 inhibitor	Deutetrabenazine (Austedo); Valbenazine (Ingrezza); Tetrabenazine (Nitoman, Xenazine)
Viral protease inhibitor	Lopinavir and ritonavir (Kaletra, Aluvia)
Source: CredibleMeds Filtered QT Drug List Rev March 01 2018 (AZCERT.ORG)	

Definition: A Disorder Characterized by Frequent and Watery Bowel Movements.	
1	Increase of <4 stools per day over baseline; mild increase in ostomy output compared to baseline
2	Increase of 4 – 6 stools per day over baseline; moderate increase in ostomy output compared to baseline
3	Increase of \geq 7 stools per day over baseline; incontinence; hospitalization indicated; severe increase in ostomy output compared to baseline; limiting self-care ADL
4	Life-threatening consequences; urgent intervention indicated
5	Death

Appendix 9 - Common Terminology Criteria for Adverse Events: Diarrhea (Version 4.03)

Appendix 10 - Investigator Responsibilities, Required Documentation, and Signature

CTI BioPharma Corp. will select the investigator(s) on the basis of their expertise in the field of clinical studies in hematologic oncology and in the care and treatment of patients with chronic myeloproliferative diseases. Investigators will also be selected on the appropriateness of their facility to conduct a research study of this nature, and the characteristics of the patient population treated at the institution. The investigator will:

- Obtain Institutional Review Board (IRB), Research Ethics Board (REB), or Independent Ethics Committee (IEC) approval of the protocol and amendments to the protocol and Informed Consent Form before initiation of the protocol or any amendments for the study, and obtain annual IRB or IEC renewal, as required.
- Ensure that current FDA and/or ICH-E6 regulations are followed.
- Select all patients in accordance with the selection criteria outlined in the study protocol.
- Treat and follow patients as described in this research protocol. Complete all electronic case report forms (eCRFs) in a timely manner and review eCRFs for accuracy and completeness. Provide the original clinical source documents to verify all data entered on eCRFs or SAE reports and all data that document the course of the patient throughout their participation on the study. Provide a clinical summary to the Sponsor's clinical research monitor.
- Report all adverse events to CTI BioPharma Corp. or designee, as required by the protocol.
- Ensure that the investigational drug is kept in a secured, limited access area and stored under proper conditions. Ensure that all investigational drug receipt and dispensing information is recorded and all drug can be accounted for at all times.
- Before initiation of the study, each participating investigator will submit to CTI:
 - FDA Form 1572 and, if applicable, other ministry of health required forms
 - Copies of the medical licenses of principal investigators and subinvestigators
 - Addresses and descriptions of all clinical laboratory facilities to be used
 - Laboratory certification and expiration dates
 - Normal ranges and effective dates for all required laboratory tests
 - IRB/REB/IEC approval letter referencing the protocol (and amendments, if applicable).

Appendix 11 - Patient Global Impression Assessment

Patient Global Impression Assessment

Patient Number: Today's date (day/month/year): / /

Instructions: Circle the answer that is most appropriate.

Since the start of the treatment you've received in 1. Very much improved this study, your myelofibrosis symptoms are:

- 2. Much improved
- 3. Minimally improved
- 4. No change
- 5. Minimally worse
- 6. Much worse
- 7. Very much worse

12.2.2 Transfusions	21
12.2.3 ECOG Performance Status	21
13 Safety Analyses	22
13.1 Adverse Events	22
13.2 Clinical Laboratory Measurements	23
13.3 Other Clinical Safety	23
13.3.1 Electrocardiogram (ECG)	23
13.3.2 Echocardiogram or Multiple-gated Acquisition Scan	24
13.3.3 Vital Sign Measurements	24
13.3.4 Physical Examinations	26
13.3.5 Supplemental Procedures	26
13.3.6 Progressive Disease	26
13.3.7 Subgroup Analysis of Safety	26
14 Genetic Background	26
15 Pharmacokinetic and Pharmacodynamic Analyses	26

16	Determination of Sample Size	26
17	Data Handling Rules	27
17.1	Definition of Baseline Value	27
17.2	Partial Current MF Diagnosis Date	27
17.3	Partial or Missing AE Onset and Resolution Dates.....	27
17.4	Partial or Missing Transfusion Dates	28
17.5	Partial or Missing Concomitant Medication and Supplemental Procedure Dates.....	28
12.1	Analysis Windows.....	29
12.2	Laboratory Results Reported as a Range.....	30
13	References.....	30

Modification	Rationale
Restructured the layout of the SAP to include separate sections for variables definitions and analyses	Reorganization of this document aimed to improve the presentation of the statistical analysis information.
Added data convention	Added details on the data conventions that will be used for data reporting.
Disposition	Added details and clarification of data summaries
Updated the Safety Population	The safety population was modified to define the subject's actual treatment as the initial dose taken since per protocol dose could have been modified (reduced).
PK/PD analyses	These analyses were removed from the statistical analysis plan as a separate PK/PD analysis plan is available.
Excluded the Per Protocol Population and modified the Full Analysis Population to evaluate randomized and treated patients and not condition on having available endpoint data at Week 24.	Following a conservative approach in order to be more data inclusive these populations were modified (excluded) in order to include all randomized and treated subjects in the analysis.
Added reporting of the Progressive Disease information and Physical Examination	Data on progressive disease and physical examinations were collected throughout the study however data reporting was not specified in previous SAP versions.
Excluded TSS evaluation of treatment effects (GEE analysis) and the dose response using the moving average.	The primary aim of this study is to establish the optimal dose with no plan for a formal statistical hypothesis testing. GEE analysis is not considered integral to evaluate the study efficacy objectives
Excluded '30 day Post-EOT' visit from the evaluation of 'worst' value at post-baseline	Safety measures are focused on assessments performed while on study treatment or within 30 days after treatment ended.
Exclusion of the Interim Analysis	The implementation of the BPP futility rule in PAC203, based on spleen volume reduction (SVR), was flawed as assumptions for SVR were based on response rates observed in the completed Phase 3 studies. This misrepresents the population under study in PAC203. For instance, some patients in the PERSIST-2 population had prior JAK inhibitor exposure, however all patients enrolled in the PAC203 study must have prior JAK inhibitor exposure.

	Following mid-year 2018 meetings with the FDA and EMA, and in consultation with the IDMC, the interim efficacy analysis based on a BPP futility rule of SVR was removed so that the study objective of identifying an optimal dose is informed by efficacy, safety, pharmacokinetic and pharmacodynamic data from a fully enrolled study.
Expanded the analysis windows of the SPV, TSS and PGIC	To minimize missing data while keeping clinical relevance.
Expanded the windows of the labs and vital signs information	A modification to the 'EOT' and '30 day-post EOT' analysis windows was made to align the safety assessments with the visit schedule as specified in the protocol calendar of assessments.
Added ECG categories and plots	Following the E14 clinical evaluation of QT/QTc interval prolongation and proarrhythmic safety guidelines
Added information to the prior and concomitant medication definitions section	Added the definitions for prior and concomitant medications and specified reports by myelofibrosis indication
Added ECOG definition and reports	Added information on the EGOC scale and the definition for each category. In addition added the summary reports.
Added PGIC and spleen variables definitions	These efficacy variables were not defined previously in the document however analyses of this information was specified in the protocol.
Subgroups of Efficacy	Clarification of clinically meaningful groups
Added information on imputation of the concomitant medications and transfusions	Added instruction for handling missing dates for prior and concomitant medications as well as for transfusions.

1. SCOPE

This document describes the statistical analyses and data presentations to be performed for protocol PAC203, “An Open-Label, Randomized, Phase 2 Dose-Finding Study of Pacritinib in Patients with Primary Myelofibrosis, Post-Polycythemia Vera Myelofibrosis, or Post-Essential Thrombocythemia Myelofibrosis Previously Treated with Ruxolitinib”.

This statistical analysis plan (SAP) provides a detailed description of the strategy, rationale, and statistical techniques to be used to determine the most appropriate dosage of pacritinib for future studies. It provides additional details concerning the statistical analyses that were mentioned in the protocol. If additional analyses are required to supplement the planned analyses described in this SAP, they will be identified as post hoc in the clinical study report.

2. STUDY OBJECTIVES AND HYPOTHESES

2.1 STUDY OBJECTIVES

2.1.1 Primary Objective

The primary objective is to determine a recommended dosage of pacritinib for further clinical studies.

2.1.2 Secondary Objectives

The secondary objectives are as follows:

1. To examine the dose-response relationship for efficacy, as measured by spleen volume reduction (SVR) using MRI or CT and total symptom score (TSS) using the Myeloproliferative Neoplasm Symptom Assessment Form Total Symptom Score version 2.0 (MPN-SAF TSS 2.0; protocol Appendix 3)
2. To examine the dose-response relationship for safety with a focus on AEs of interest
3. To further characterize the pharmacokinetics (PK) and pharmacodynamics (PD) of pacritinib
4. To evaluate the long term efficacy and safety of pacritinib treatment

1.1 Hypotheses

As this study is designed to explore the dose-response relationship for pacritinib among primary and secondary myelofibrosis (MF) patients and to determine a recommended dosage for further clinical studies, there is no formal statistical hypothesis to be tested.

3. SUMMARY OF STUDY DESIGN

This is a dose-finding study in patients with myelofibrosis who were previously treated with ruxolitinib, are highly symptomatic (DIPSS risk score of Intermediate-1 to High Risk), and have splenomegaly (assessed by physical examination). The study is designed to support a pacritinib dosage selection decision, the process of which will be based on pre-specified efficacy and safety parameters and assessed by an independent data monitoring committee (IDMC).

Spleen volume will be measured by MRI or CT at baseline and Weeks 12 and 24. Safety will be monitored with physical examinations, clinical laboratory assessments (including hematologic, chemistry, and coagulation testing), and cardiac monitoring (including ECG and echocardiogram testing); specified study treatment dosage modifications will be followed to address identified abnormalities. Adverse event data will be collected throughout the study.

Three dosages will be evaluated; pacritinib 100 mg QD, pacritinib 100 mg BID, and pacritinib 200 mg BID. During the study, the interim data will be reviewed by the IDMC for the determination of dropping treatment arm(s), which will be guided by

- The results of interim analyses evaluating the Bayesian predictive probability (BPP) of clinically meaningful SVR (details in section 7.4),
- Safety reviews, with occurrence of 2 treatment-emergent CTCAE grade ≥ 4 cardiac AEs or 2 treatment emergent CTCAE grade ≥ 4 hemorrhage AEs in any arm being of particular concern, and
- Other efficacy and safety measures.

Assigned treatment will continue for 24 weeks unless the patient experiences progressive disease, intolerable AEs, or withdraws consent, or until the assigned treatment arm is closed. Once an arm is closed, patients in that arm will discontinue the study. No study treatment crossover will be allowed. The maximum duration of trial participation for an individual patient will be approximately 3 years.

4. RANDOMIZATION AND BLINDING

Initially, eligible patients will be centrally randomized in a 1:1:1 allocation ratio to pacritinib 100 mg QD, pacritinib 100 mg BID, or pacritinib 200 mg BID using a central interactive web response system (IWRS). If interim analysis indicates that any one of the treatment arm meets the stopping

criteria (protocol Sections 11.8 and 11.9) for efficacy or safety and is thus dropped, then the randomization will be updated to a 1:1 ratio of the two remaining study arms. In the case of two arms being dropped by interim efficacy or safety monitoring, all eligible patients will be enrolled to the remaining one active arm until up to 30 evaluable subjects are enrolled in that arm. The dropping of a treatment arm is effected in the IWRS by disabling randomization to the relevant treatment arm. Thus, the treatment arm being dropped will not be available as an option for treatment assignment at randomization.

The randomization will be stratified by geographic region (North America vs. Europe vs. rest of the world (RoW)) and baseline platelet count ($\leq 50,000/\mu\text{L}$ vs. $> 50,000/\mu\text{L}$ to $\leq 100,000/\mu\text{L}$ vs. $> 100,000/\mu\text{L}$). Permuted blocks of size 3 will be used within each stratum to balance the treatment allocation. The treatment codes and descriptions for the treatment arms are:

- 1: PAC 100 mg QD (100 mg of pacritinib once daily)
- 2: PAC 100 mg BID (100 mg of pacritinib twice daily), and
- 3: PAC 200 mg BID (200 mg of pacritinib twice daily).

This study is an open-label study. A patient's treatment assignment will be known to all except the independent radiographic and cardiology assessors who will remain blinded to patient treatment assignment throughout the study.

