This is a dose-finding study in patients with primary or secondary MF (DIPSS risk score of Intermediate-1 to High-Risk) who were previously treated with ruxolitinib. The study is designed to support a pacritinib dosage selection decision. Three dosages will be evaluated, with patients randomized 1:1:1 to pacritinib 100 mg QD, pacritinib 100 mg BID, or pacritinib 200 mg BID. Randomization will be stratified by baseline platelet count $(\leq 50,000/\mu L; > 50,000/\mu L and \leq 100,000/\mu L; and > 100,000/\mu L)$. The most recent platelet count obtained prior to start of treatment will be the basis of stratification by baseline platelet count. Assigned treatment will continue until the patient experiences progressive disease, intolerable AEs, withdraws consent, or until the assigned treatment arm is closed. No study treatment crossover will be allowed. All patients should complete all visit procedures through Week 24, including patients who stop pacritinib treatment or have protocoldefined progressive disease prior to Week 24, unless patient withdraws consent, dies, undergoes splenic irradiation or splenectomy, or initiates any non-protocol-directed anti-myelofibrosis treatment. Following regulatory, EC or IRB approval of Amendment 6, study treatment for patients at and beyond the week-24 timepoint will terminate. Study assessments will cease following the End-of-Treatment (EOT) or 30-day post EOT visit, as applicable. Patients who are benefiting from therapy as of study treatment termination may be allowed to continue receiving pacritinib under single patient expanded access or named patient programs at the investigator's discretion and subject to regulatory, Ethics or IRB approval.

The dosage selection process will be based on efficacy and safety parameters, including model-based dose-response.

This study will utilize planned frequent monitoring by an IDMC. At a minimum, the IDMC will consist of 1 board-certified hematologist, 1 board-certified cardiologist, and 1 biostatistician experienced in adaptive design clinical trials. The roles and responsibilities of the IDMC will be fully defined within the IDMC charter, including, but not limited to:

- Review safety data across arms, focusing on bleeding events, cardiac events, and deaths
- Evaluate cumulative safety as described in Section 11

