4.2 Criteria for Withdrawal of Patients

4.2.1 Withdrawal from Study Treatment and Procedures

Patients may discontinue or be withdrawn from treatment at any time. All reasonable efforts should be made to retain patients who discontinue treatment in the study and to conduct visits through Week 24 required by the protocol, including MRI (preferred) or CT scanning and follow-up for progressive disease, and leukemic transformation. Reasons for discontinuing treatment may include but are not limited to the following:

- Documented disease progression as defined in Section 3.2.
- Unrelated intercurrent illness that, in the judgment of the principal investigator, will affect assessments of clinical status to a significant degree
- Pregnancy
- Patient's decision
- Patient noncompliance with study drug
- Clinical need for concomitant therapy that is not permitted in the study
- Decision on the part of the investigator or CTI BioPharma Corp. medical monitor that it is in the patient's best interest to withdraw from study treatment
- Sponsor decision to terminate study
- Death

5 Method of Treatment Assignment and Blinding

Initially, eligible patients will be centrally randomized in a 1:1:1 allocation ratio to pacritinib 100 mg QD, pacritinib 100 mg BID, or pacritinib 200 mg BID using a central interactive web response system. If interim monitoring analysis indicates that any one of the treatment arm meets the stopping criteria (Section 11.9) for efficacy or safety and is thus dropped, then the randomization will be updated to a 1:1 ratio of the two remaining study arms. In the case of two arms being dropped by interim efficacy or safety monitoring, then all eligible patients will be enrolled to the remaining one active arm until up to 30 evaluable subjects are enrolled for that arm.

Randomization will be stratified by geographic region (North America, Europe, versus rest of the world [ROW]) and baseline platelet count (\leq 50,000/µL; >50,000/µL and \leq 100,000/µL; and >100,000/µL). The most recent platelet count obtained prior to start of treatment will be the basis of stratification by baseline platelet count.

A patient's treatment assignment will be known to all except the independent radiographic and cardiology assessors who will remain blinded to patient treatment assignment throughout the study.

6 Study Treatment

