12 EFFICACY ENPOINTS AND ANALYSES

12.1 PRIMARY EFFICACY ENPOINTS

12.1 1 Spleen Volume Reduction

The primary efficacy variable for dosage selection is the percent reduction in spleen volume from baseline as measured by MRI or CT at Weeks 12 and 24..

Descriptive statistics of spleen volume at baseline, Week 12, Week 24, and at End of Treatment will be presented by treatment arm. Spleen volume at End of Treatment is defined as the spleen volume collected at the end of treatment visit or the last spleen volume measured on treatment if not measured at end of treatment. Descriptive statistics of percent reduction in spleen volume at Weeks 12 and 24 and at End of Treatment will be presented by treatment arm. These descriptive statistics include counts, mean, standard deviation, standard error of the mean, median, 25th percentile, 75th percentile, minimum, and maximum. As a supportive measure of efficacy, the counts and proportions of patients with spleen volume reduction (SVR) $\geq 35\%$ at Weeks 12 and 24 and at End of Treatment will be presented by treatment arm. The exact (Clopper-Pearson) 95% confidence intervals (CIs) for the proportions will also be presented. Additional supportive analyses include imputing missing Week 24 spleen volume with the previous post-baseline (Week 12) spleen volume, if any, and repeating the above analyses. These analyses will be repeated for spleen volume measured after Week 24 in long term follow up.

12.1 2 Total Symptom Score (TSS) Analysis

Descriptive statistics of individual symptoms and TSS at baseline, every 12 weeks, and at End of Treatment will be presented by treatment arm. Descriptive statistics of percent reduction in TSS every 12 weeks and at End of Treatment will be presented by treatment arm. The counts and proportions (including Clopper-Pearson 95% CIs) of patients with TSS reduction $\geq 50\%$ every 12 weeks and at End of Treatment will be presented by treatment arm. Supportive analyses include imputing missing Week 24 TSS with the previous post-baseline (Week 12) TSS, if any, and repeating the above analyses at Week 24.

As an anchor for patient-reported symptom assessment, the patient global impression assessment (PGIA) will also be summarized and evaluated for correlation with TSS. There is 1 domain in the PGIA instrument with possible scores ranging from 1 (very much improved) to 7 (very much worse).

12.1 3 Patient Global Impression Assessment

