12.1 Subgroup Analyses of Efficacy

If there are enough patients per group, subgroup analyses may be evaluated for any potential impact of demographics or baseline disease characteristics on the efficacy endpoints. Subgroups may include, but are not limited to, baseline hemoglobin (< 100 g/L vs. ≥ 100 g/L), and baseline platelet count ($\leq 50,000/\mu\text{L}$ vs. $> 50,000/\mu\text{L}$).

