13.3.7 SUBGROUP ANALYSIS OF SAFETY

If there are enough patients per group, treatment-emergent adverse events, including all AEs, grade 3/4 AEs, and SAEs, and hematology toxicity may also be summarized by subgroups as appropriate. Subgroups may include, but are not limited to, baseline platelet count ($\leq 50,000/\mu\text{L}$ vs. $> 50,000/\mu\text{L}$) and baseline hemoglobin ($< 100 \text{ g/L}$ vs. $\geq 100 \text{ g/L}$).

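### Randomisation is stratified by region and platelet count, but no specified outcome analysis takes account of these factors or of baseline spleen volume

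*SAP*

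**What the plan says.** **Randomisation.** Under SAP Section 4, "eligible patients will be centrally randomized in a 1:1:1 allocation ratio". On stratification it states: "The randomization will be stratified by geographic region (North America vs. Europe vs. rest of the world (RoW)) and baseline platelet count". The platelet levels are up to 50,000, above 50,000 to 100,000, and above 100,000/µL, so three regions and three platelet levels make nine strata. Within them, "Permuted blocks of size 3 will be used within each stratum to balance the treatment allocation". Protocol Section 5 agrees: "Randomization will be stratified by geographic region (North America, Europe, versus rest of the world [ROW]) and baseline platelet count". The protocol synopsis and Section 3 name the platelet factor alone ("Randomization will be stratified by baseline platelet count").

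**Efficacy analysis.** SAP Section 12.1.1 says: "Descriptive statistics of spleen volume at baseline, Week 12, Week 24, and at End of Treatment will be presented by treatment arm". Percent reduction is handled the same way, and response proportions get exact intervals by arm. No covariate, stratum or between-arm contrast is specified. Protocol Section 11.4 promises 95% intervals for percent change in spleen volume, and dose-response modelling to be detailed in the SAP. The SAP sets out no such model.

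**Where the factors do appear.** SAP Section 7 tabulates enrolment by region and arm. SAP Section 8.2 lists all three platelet categories at baseline.

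**Subgroups.** The SAP section on subgroup analyses of efficacy says "Subgroups may include, but are not limited to, baseline hemoglobin" and goes on to platelets, split at 50,000/µL. SAP Section 13.3.7 says "hematology toxicity may also be summarized by subgroups as appropriate" and gives the same platelet split. Region is named in neither list.

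**The concern.** Stratifying makes the arms alike on region and platelets, which reduces the chance variation in a comparison of arms. A standard error from raw arm summaries does not reflect that reduction. Anyone who builds a dose-difference interval from the planned means and standard deviations will therefore understate what the design delivers. Baseline spleen volume is a separate matter: it was not balanced by design, so if it predicts percent reduction, leaving it out forgoes real precision.

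The study exists to choose among three doses, and percent spleen volume reduction is the primary efficacy variable for that choice. How sharply the doses are separated is what the reader of the report will want to know.

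A smaller issue is the named platelet subgroup, which pools the middle and upper randomised levels. By the protocol's account, PERSIST-2, which supplied the 200 mg BID data, enrolled patients at or below 100,000/µL. A summary that crosses that boundary cannot show whether results above it resemble those below.

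**Working it through.** **Inputs.** SD of percent reduction 20 points and 30 evaluable patients per arm (protocol Section 11.7, SAP Section 16); up to 50 enrolled per arm (protocol Section 11.7); nine strata, blocks of three (SAP Section 4). The share of variance explained, R², is in neither document and is an assumption, taken from 0 to 0.30.

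**The plan's own figures.** None depends on the strata. The safety figures reproduce: 1 − 0.95^50 = 92.3% (protocol: 92%) and 1 − 0.95^30 = 78.5% (SAP: 78%).

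**Step 1: what raw summaries would report.** The standard error of a difference between two arms is SD × √(2/n) = 20 × √(2/50) = 4.00 points.

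**Step 2: the true standard error under stratification.** A simulation of 1:1:1 blocks of three in nine strata (50 per arm, 2,000 replicates, no dropout) gave:

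| R² of strata | True SE, raw | True SE, adjusted | 4.00 ÷ true raw SE | Coverage of raw 95% interval |
|---|---|---|---|---|
| 0 | 3.93 | 3.95 | 1.02 | 95.5% |
| 0.10 | 3.82 | 3.82 | 1.05 | 96.3% |
| 0.20 | 3.63 | 3.61 | 1.10 | 96.9% |

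Simulation error in each SE is about 1/√(2 × 2,000) = 1.6%, so the first row is consistent with no discrepancy. The raw and adjusted estimates are about equally precise. Only the reported raw SE is off, by about 5% at R² = 0.10 and 10% at 0.20. The mean error of the raw difference was within 0.1 point in every row.

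**Step 3: interval width.** The 95% half-width is t × 20 × √(1 − R²) × √(2/n), with 3n − 3 degrees of freedom raw and 3n − 7 after adding platelet level and region:

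| R² | n = 50 per arm | n = 30 per arm |
|---|---|---|
| Raw interval | 7.90 | 10.26 |
| Adjusted, 0 | 7.91 | 10.27 |
| Adjusted, 0.05 | 7.71 | 10.01 |
| Adjusted, 0.10 | 7.50 | 9.74 |
| Adjusted, 0.20 | 7.07 | 9.19 |
| Adjusted, 0.30 | 6.62 | 8.59 |

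For the strata, this narrowing corrects an interval that was too wide.

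**Step 4: baseline spleen volume.** Randomisation does not balance it, so here the true SE falls, by 1 − √(1 − R²): 0.051 at R² = 0.10, 0.106 at 0.20, 0 at 0. A simulation at R² = 0.10 agrees, with the SE falling from 4.01 to 3.80 (3.80/4.01 = 0.948).

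**Step 5: three platelet levels.** If the levels were equal in size (an assumption), each would hold about 50/3 ≈ 17 patients per arm, and the half-width for an arm mean is 2.12 × 20/√17 = 10.3 points. With 30 per arm it is 10 patients and 14.3 points. The pooled upper group would hold about 33 or 20 patients, with half-widths of 7.1 or 9.4.

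**The case against.** **The study is descriptive.** No hypothesis is tested and no between-arm contrast is planned, so no planned interval is made wrong. This stands, and it limits the point to an improvement. Still, choosing a dose means comparing arms, and the protocol promises both intervals for percent change and a dose-response model.

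**R² may be close to zero.** The protocol's background section reports that spleen response to pacritinib in PERSIST-1 was not affected by baseline thrombocytopenia. Nothing in the documents shows that baseline volume predicts percent change, and the endpoint is already relative to baseline. This stands too: at R² = 0 nothing is gained, and almost nothing is lost (7.91 against 7.90).

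**Model-based intervals for single arm means can be too narrow.** They treat the stratum mix as fixed. In a simulation with about 51 per arm and three equal platelet strata explaining 30% of variance, the model reported an SE of 2.34 when the true value was 2.55; the raw SE reported 2.80 when the true value was 2.56. Comparative precision should therefore be read from the dose differences.

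**The subgroup lists are optional and open-ended.** Three-level tables are already permitted, and the 50,000/µL cut has a rationale, since the protocol singles out patients at or below it for weekly platelet monitoring. Hence the three-level display is an addition and not a correction.

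**Stronger readings.** A reader might infer that the strata are used nowhere. They do appear in the enrolment and baseline tables, and the separate PK/PD plan is not among the documents, so its covariates are unknown. A reader might also infer that ignoring the strata blurs the dose effect. Balance within strata is built in, and the simulated raw difference is unbiased.

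**Conclusion.** The gap is real and modest. No specified outcome analysis accounts for the randomisation factors or for baseline spleen volume. For the strata, the consequence is a dose-difference interval that is too wide, with a standard error about 5% too large at R² = 0.10, about 10% at 0.20 and correct at 0. For baseline spleen volume, adjustment would reduce the true standard error by about 5% at 0.10, 11% at 0.20 and nothing at 0.

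It is tempting to translate R² into patients: 1/(1 − R²) − 1 gives 11%, 25% and 43% more at 0.10, 0.20 and 0.30. That does not hold for stratum adjustment, because the stratified blocks have already put that precision into the raw estimate. It could hold only for baseline spleen volume, and only if that variable is as prognostic as assumed.

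The result rests on an SD of 20, 50 per arm, complete scans and assumed R² values. Balance is assured at randomisation. Whether it persists among patients with a Week 24 scan is a separate missing-data question that this calculation does not address.

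**What to change.** 1. In SAP Section 12.1.1, beside the raw summaries, add a linear model for percent spleen volume reduction at Weeks 12 and 24. Include arm, the three platelet strata and region as randomised, and baseline spleen volume. Report adjusted arm means and pairwise dose differences with 95% intervals. Keep them descriptive, and state that the arm-mean intervals are conditional on the enrolled mix.
2. As a minor addition, in the SAP section on subgroup analyses of efficacy and in Section 13.3.7, show by-arm summaries for the three randomised platelet levels alongside the existing two-level cut, not in place of it. Label them descriptive because the cells are small: about 17 per arm if equal, with a half-width of about 10 points.
3. Reconcile the protocol synopsis and Section 3 with Section 5 on whether region is a stratification factor, so that the model matches the randomisation.

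The cost is document wording and programming. Every variable is already collected, and no planned output is removed.
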